## 2.2. Study Objectives

*The primary objectives of this study are:*

- *To determine the safety and efficacy of fesoterodine 4 mg and 8 mg PR following once daily treatment for 12 weeks in pediatric NDO subjects with weight >25 kg.*
- *To determine the safety and efficacy of fesoterodine 2 mg and 4 mg following once daily treatment for 12 weeks in pediatric NDO subjects with weight  $\leq$ 25 kg.*

*The secondary objectives of this study are to:*

- *evaluate the safety and efficacy of fesoterodine PR versus oxybutynin in pediatric NDO subjects with weight >25 kg.*
- *evaluate the safety of fesoterodine 4 mg and 8 mg PR once daily treatment for up to 24 weeks in pediatric NDO subjects with weight >25 kg.*
- *evaluate the safety of fesoterodine 2 mg and 4 mg BIC once daily treatment for up to 24 weeks in pediatric NDO subjects with weight  $\leq$ 25 kg.*
- *determine the steady-state population pharmacokinetics of 5-HMT following fesoterodine 4 mg and 8 mg PR once daily treatment in pediatric NDO subjects with weight >25 kg.*
- *determine the steady-state population pharmacokinetics of 5-HMT following treatment with two doses of fesoterodine 2 mg and 4 mg BIC treatment once daily in pediatric NDO subjects with weight  $\leq$ 25 kg.*

## 3. INTERIM ANALYSES, FINAL ANALYSES AND UNBLINDING

*A blinded interim analysis may be performed after approximately 50% of randomized subjects in Cohort 1 have completed the active comparator phase of the study and provided data for the primary endpoint (including the corresponding baseline value) as a tool to reassess the sample size. The sample size will be recalculated based on the variability of the primary endpoint obtained from this analysis. Even though this is an open label study, data utilized in this interim analysis will remain blinded to treatment allocation to minimize bias. Based on this, the study statistician and clinician will assess whether an adjustment to the sample size is required.*

*These results will not be used to modify the design of the study, other than a potential adjustment to the sample size. No adjustment will be made to the nominal p-values to account for this analysis. The results of this analysis will not be made available to the investigator and site staff, other than to inform them of any adjustment to the sample size that is recommended. A similar blinded interim analysis may be performed after approximately 50% of randomized subjects in Cohort 2 have completed the efficacy phase of the study.*

*This study will use an External Data Monitoring Committee (EDMC) for the purpose of protecting the safety of patients by regular independent assessment of risk/benefit during the conduct of the study (for each cohort separately as well as combined).*

*The EDMC will meet at specified intervals during the study to assess its progress including the safety data and/or critical efficacy endpoints. Safety data will include assessment of adverse events, vision testing, CBCL/GPT assessments, vital signs including heart rate, incidence of urinary tract infection (as evidenced by urinalysis, urine microscopy and culture), clinical laboratory evaluations in the context of age-appropriate norms, with particular reference to liver function tests and renal chemistry, and post-void residual volume (PVR) in subjects not performing CIC, or with >1 urinary tract infection (UTI) during the study.*

*Assessment of adverse events of particular interest will include, but not be limited to, anticholinergic effects such as dry mouth, dry eyes and constipation, CNS effects such as behavioral changes (eg, aggression), decreased cognitive function, headache, seizures, somnolence and visual effects such as accommodation disorder, blurred vision, and amblyopia,*

*The remit of the EDMC will be to, and to recommend whether to continue or, modify, or stop the study. In the event that a negative benefit-risk is determined, the EDMC may recommend that the study (or recruitment to a particular cohort) be terminated. The EDMC will be advisory to the sponsor, Pfizer Inc. The sponsor will promptly review the EDMC recommendations, and will make decisions regarding accepting, modifying or rejecting those recommendations. The final decisions regarding trial continuation, modification or termination will be made by the sponsor.*

*Full technical details for the EDMC, including its primary responsibilities, relationship with other trial components, membership, timing of meetings, and rules will be provided in the EDMC Charter, which will be drawn up by the sponsor study team and agreed to by the EDMC. All members included in an EDMC must have acceptable conflict of interest status and a contract should be in place before the work commences.*

The final analysis will be performed following official database release, once all subjects have completed the whole study.

## **4. HYPOTHESES AND DECISION RULES**

### **4.1. Statistical Hypotheses**

The following hypotheses are applicable only to the analyses of the heavier (>25 Kg) Cohort 1, as there is no formal hypothesis testing planned for the lighter ( $\leq 25$  Kg) Cohort 2

Null Hypothesis: The difference between baseline and week 12 in maximum cystometric bladder capacity is equal to zero.

Alternative Hypothesis: The difference between baseline and week 12 in maximum cystometric bladder capacity is not equal to zero.

### Sample Size Determination

#### *Cohort 1 (>25 kg)*

*A sample size of 33 evaluable subjects per group is sufficient to give a power of at least 90% to detect a change from baseline of 70 mL in the primary endpoint, maximum cystometric capacity (MCC), when the standard deviation of the change from baseline is 120 mL. This calculation assumes the testing will be performed at a two-sided 5% significance level and is based on results observed from the two highest dose periods (each 4 weeks) in previous tolterodine neurogenic bladder studies 583E-URO-0581-001, 583E-URO-0581-002 and 583-URO-0581-003, as well as published data from studies of oral oxybutynin in neurogenic bladder subjects. An oxybutynin active comparator arm will enable comparisons between fesoterodine and oxybutynin to be made; therefore a sufficient number of subjects will be randomized into Cohort 1 to ensure a total of approximately 99 subjects (33 evaluable subjects per arm) are evaluable at Week 12.*

*This sample size will also provide a 2-sided 95% confidence interval for the change from baseline in MCC of approximately  $\pm 70$  mL around the point estimate for the difference between each fesoterodine arm and oxybutynin, with 90% coverage probability. Using this estimation approach, these confidence intervals will be used to assess the comparability of each fesoterodine dose and oxybutynin.*

#### *Cohort 2 ( $\leq 25$ kg)*

*A sample size of approximately 25 evaluable subjects per arm will provide a 2-sided 95% confidence interval for the change from baseline in maximum cystometric capacity (MCC) of approximately  $\pm 55$  mL around the point estimate for the mean, with 80% coverage probability. This assumes a standard deviation of 120 mL. This is based on results observed from the two highest dose periods (each 4 weeks) in previous tolterodine neurogenic bladder studies 583E-URO-0581-001, 583E-URO-0581-002 and 583-URO-0581-003, as well as published data from studies of oral oxybutynin in neurogenic OAB patients. It is planned that a sufficient number of subjects will be randomized into this cohort to ensure a total of approximately 50 subjects (25 evaluable subjects per arm) are evaluable at Week 12.*

### 4.2. Statistical Decision Rules

Changes from baseline in Cohort 1 will be tested at the  $\alpha=0.05$  level, and 95% Confidence Intervals will be estimated for Cohort 2.

### 5. ANALYSIS SETS

*The following efficacy analysis sets will be determined separately for each cohort.*

### 5.1. Full Analysis Set

*The Full Analysis Set will include all subjects who have been randomized and received at least one dose of study medication and have provided baseline primary endpoint data.*

This is to utilize as much data as possible from any subjects with urodynamic data available for analysis and will not exclude subjects with only baseline data available.

### 5.2. Per Protocol Analysis Set

*The Per Protocol Analysis Set will include all subjects who have completed the active comparator/efficacy phase of the study, and who have not violated any of the inclusion/exclusion criteria or deviated from the protocol in a way that could affect the efficacy outcome of the study.*

The PPAS for each cohort will be defined prior to unblinding.

#### 5.2.1. Deviations assessed prior to randomization

Violation of a major inclusion/exclusion criterion prior to randomisation would be considered a protocol violation. The criteria and determination of protocol violation/deviation will be determined by Pfizer prior to database lock.

#### 5.2.2. Deviations assessed post-randomization

Violation of a major inclusion/exclusion criterion post randomisation would be considered a protocol violation, for example:

- Initiation of a prohibited concomitant medication.
- Study drug compliance <80% or >120%.
- Incomplete primary endpoint data at week 12.

The criteria and determination of protocol violation/deviation will be determined by Pfizer prior to database lock.

### 5.3. Safety Analysis Set

There will be three safety analysis sets for Cohort 1 (to be utilized for AEs and duration of treatment summaries):

- Active Comparator Phase safety set: all subjects who received at least one dose of study medication during the active comparator phase. The following treatment assignments will be used for this analysis set:
  - Fesoterodine 4mg PR;
  - Fesoterodine 8mg PR;
  - Oxybutynin.

- Safety Extension Phase safety set: all subjects who received at least one dose of study medication during the safety extension phase. The following treatment assignments will be used for this analysis set:
  - Oxybutynin -> Fesoterodine 4mg PR;
  - Oxybutynin -> Fesoterodine 8mg PR;
  - Fesoterodine 4mg PR -> Fesoterodine 4mg PR;
  - Fesoterodine 8mg PR -> Fesoterodine 8mg PR.
- Overall study safety set: subjects who were randomized to fesoterodine during the active comparator phase and received at least one dose of study medication during both phases of the study:
  - Fesoterodine 4mg PR (24 weeks);
  - Fesoterodine 8mg PR (24 weeks).
- For all other Safety tables, the Safety Analysis Set will just consist of all subjects who received at least one dose of study medication at any time during the study (ie, in either phase). The following treatment assignments should be used for this:
  - Oxybutynin -> Fesoterodine 4mg PR;
  - Oxybutynin -> Fesoterodine 8mg PR;
  - Oxybutynin;
  - Fesoterodine 4mg PR -> Fesoterodine 4mg PR;
  - Fesoterodine 8mg PR -> Fesoterodine 8mg PR.

NB: All randomized subjects will be used for summarizing discontinuations in the Active Comparator Phase and overall, and for data collected at baseline.

There will be three safety analysis sets for Cohort 2 (to be utilized for AEs and duration of treatment summaries):

- Efficacy Phase safety set: all subjects who received at least one dose of study medication during the efficacy phase. The following treatment assignments will be used for this analysis set:
  - Fesoterodine 2mg BIC;
  - Fesoterodine 4mg BIC.
- Safety Extension Phase safety set: all subjects who received at least one dose of study medication during the safety extension phase. The following treatment assignments will be used for this analysis set:
  - Fesoterodine 2mg BIC -> Fesoterodine 2mg BIC;
  - Fesoterodine 4mg BIC -> Fesoterodine 4mg BIC.

- For all other Safety tables, the Safety Analysis Set will just consist of all subjects who received at least one dose of study medication at any time during the study (ie, in either phase). The following treatment assignments should be used for this:
  - Fesoterodine 2mg BIC -> Fesoterodine 2mg BIC;
  - Fesoterodine 4mg BIC -> Fesoterodine 4mg BIC.

NB: All randomized subjects will be used for summarizing discontinuations in the Efficacy Phase and overall, and for data collected at baseline.

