#### *Cohort 1 (Subjects >25 kg)*

For this cohort this is a randomized, open label, active comparator parallel group study with three treatment arms.

Note: The first week of the fesoterodine 8 mg group will be at a dose of 4 mg each day, for the active comparator phase and for those subjects changing from oxybutynin to the safety extension phase.

[figure not shown]
The study consists of two parts: a 12 week three arm phase with an active comparator (oxybutynin XL), followed by a 12 week two arm extension phase without the active comparator.

There is a variable screening period (minimum 3 days) prior to the baseline visit, the duration of which is principally determined by the prior medication subjects may need to washout ([Appendix 3](#)). At baseline, subjects will be randomized to one of three arms: 4 mg or 8 mg/day of fesoterodine or oxybutynin XL. Subjects will be randomized to each arm in a 1:1:1 ratio.

After 12 weeks (or earlier if appropriate), subjects in the oxybutynin arm of the study will be allocated by the investigator to fesoterodine at either 4 mg or 8 mg/day.

A sufficient number of subjects will be randomized into Cohort 1 to ensure a total of approximately 99 subjects (approximately 33 evaluable subjects per arm) are evaluable for the primary efficacy and safety analyses at Week 12, after which screening to Cohort 1 will be closed.

*Cohort 2 (Subjects  $\leq 25$  kg)*

Note: The first week of the fesoterodine 4 mg group will be at a dose of 2 mg each day, for the efficacy phase.

For this cohort the study consists of two parts: a 12 week two arm efficacy phase, followed by a 12 week two arm safety extension phase.

There is a variable screening period (minimum 3 days) prior to the baseline visit, the duration of which is principally determined by the prior medication subjects may need to washout ([Appendix 3](#)).

At baseline, subjects will be randomized to one of two fesoterodine treatment arms: doses 2 mg and 4 mg/day). Subjects will be randomized to each arm in a 1:1 ratio. Once allocated subjects will remain on that dose for the 12 week efficacy phase, and will continue at the same dose during the 12 week safety extension phase.

It is planned that a sufficient number of subjects will be randomized into this cohort to ensure a total of approximately 50 subjects (approximately 25 evaluable subjects per arm) are evaluable for the primary efficacy and safety analyses at Week 12, after which screening to Cohort 2 will be closed.

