#### *Cohort 2 (Subjects ≤25 kg)*

Subjects will be randomized to either 2 mg or 4 mg fesoterodine BIC capsules once daily throughout the initial 12 weeks of the efficacy phase and will continue at the same dose during the 12 week safety extension phase. All those assigned to the fesoterodine 4 mg arm will start at 2 mg daily for one week and will then escalate to 4 mg daily. If subjects cannot tolerate the doses they are randomized to, they should be withdrawn from the trial as a dose reduction is not permitted on this trial.

For both cohorts, it is expected that all subjects will also complete the extension phase unless, in the judgment of the investigator, this is not appropriate. Subjects can withdraw from the study at any time.

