### **5.2. Oxybutynin (Subjects >25 kg)**

Subjects in Cohort 1 (weight >25 kg) randomized to oxybutynin will receive oxybutynin extended release (XL) tablets at a starting dose in accordance with approved pediatric labeling, and accepted practice eg, oxybutynin XL 5 mg once a day. Dose optimization will be achieved by either up or down titration in 5 mg increments on an approximately weekly basis to achieve a balance of efficacy and tolerability. All subjects should achieve a minimum total daily dose of oxybutynin XL 10 mg by the end of the dose adjustment period

at Week 4. The maximum dose used in this study will not exceed the recommended dose consistent with approved pediatric labeling, and accepted practice. Subjects who were on oxybutynin prior to study entry and who are randomized to the oxybutynin XL treatment group may, at the discretion of the investigator, restart at the equivalent pre-study total daily dose.

After Week 4, subjects taking oxybutynin XL should remain on the same dose for the subsequent 8 weeks of the study, and no further dose adjustments should be permitted. Subjects who are unable to tolerate a minimum total dose of oxybutynin XL 10 mg once daily should be withdrawn. Subjects who withdraw from the oxybutynin treatment arm for reasons of toleration, and who fulfill all continuation criteria, may be directly allocated by the investigator to fesoterodine treatment at either 4 mg or 8 mg/day for the remaining 12 week safety extension period. All those assigned to the fesoterodine 8 mg arm will start at 4 mg daily for one week, and will then escalate to 8 mg daily. All subsequent study visits should be scheduled relative to the start of the extension phase.

At Visit 5 (or earlier if appropriate), subjects in the oxybutynin arm of the study will be allocated by the investigator to fesoterodine at either 4 mg or 8 mg/day. Subjects should undergo a minimum 2 day washout period from oxybutynin prior to starting treatment with Fesoterodine. All those assigned to the fesoterodine 8 mg arm will start at 4 mg daily for one week, and will then escalate to 8 mg daily. Once allocated the dose will remain fixed for the period of the extension; if treatment is inadequate or the subject cannot tolerate the dose, consideration should be given to withdrawal.

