### **Other Adverse Event Reporting**

Adverse events will be reported separately for the active comparator phase, the safety extension phase and over the entire study. Summaries will be presented as follows:

For the Active Comparator/Efficacy Phase:

The active comparator/efficacy phase is defined as the first dose up to week 12 if the subject continues into the Safety Extension Phase. If a subject has discontinued early during the active comparator/efficacy phase, the reporting period for this phase will be up to their last dose of study medication plus the drug specific lag time. For Fesoterodine this will be 7 days, however for Oxybutynin (Cohort 1 only) this will be either 2 days or the time until first treatment of Fesoterodine in the safety extension phase, whichever is longer. The following treatment groups will be summarized.

Cohort 1:

Fesoterodine 4mg PR

Fesoterodine 8mg PR

Oxybutynin

Cohort 2:

Fesoterodine 2mg BIC

Fesoterodine 4mg BIC

For the Safety Extension Phase:

The safety extension phase is started after the first dose of fesoterodine in the safety extension phase is administered. Only adverse events that started or worsened in the Safety Extension phase would be counted as treatment emergent in this phase. Note that treatment emergent AEs will be defined as described in the Pfizer Data Standards for cross over studies. The following treatment groups will be summarized.

Cohort 1:

Oxybutynin -> Fesoterodine 4mg PR

Oxybutynin -> Fesoterodine 8mg PR

Fesoterodine 4mg PR -> Fesoterodine 4mg PR

Fesoterodine 8mg PR -> Fesoterodine 8mg PR

Cohort 2:

Fesoterodine 2mg BIC -> Fesoterodine 2mg BIC

Fesoterodine 4mg BIC -> Fesoterodine 4mg BIC

For the whole study (overall):

These presentations will only include subjects who were randomised to fesoterodine.

Cohort 1:

Fesoterodine 4mg PR (24 weeks)

Fesoterodine 8mg PR (24 weeks)

Cohort 2:

Fesoterodine 2mg BIC (24 weeks)

Fesoterodine 4mg BIC (24 weeks)

Plots displaying the point estimate for the percentage of subjects in each treatment group who experience adverse events of particular interest will be presented for the Safety Extension phase and for the study as a whole.

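### Cohort 1 has no adverse event summary covering every child exposed to fesoterodine; a supplementary any-exposure table should be added beside the 24-week tables

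*SAP*

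**What the plan says.** SAP 5.3 gives Cohort 1 three safety sets for AEs and duration of treatment. The third is the "Overall study safety set: subjects who were randomized to fesoterodine during the active comparator phase". A further condition for entry is that the child "received at least one dose of study medication during both phases of the study". Its two columns are fesoterodine 4 mg PR and 8 mg PR, each labelled 24 weeks.

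SAP 8.2.5 (Other Adverse Event Reporting) says of the whole-study AE tables: "These presentations will only include subjects who were randomised to fesoterodine". It does not repeat the both-phases condition. It plans plots of events of particular interest for the extension phase and for the study as a whole.

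Protocol 5.2 provides for the switch, which is due at the Week 12 visit but can come sooner: "subjects in the oxybutynin arm of the study will be allocated by the investigator to fesoterodine at either 4 mg or 8 mg/day". SAP 5.3 and 8.2.5 report these children's fesoterodine-period AEs in the extension-phase set, in two columns of their own (oxybutynin to 4 mg, oxybutynin to 8 mg). Three-tier AE reporting covers only the active comparator phase.

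A secondary objective in SAP 2.2 is to "evaluate the safety of fesoterodine 4 mg and 8 mg PR once daily treatment for up to 24 weeks". The only pooling that SAP 8.2.5 mentions is an optional safety summary of both cohorts combined.

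**The concern.** A reader who asks how many Cohort 1 children given fesoterodine had a seizure, a behavioural change or a visual disturbance will find no planned table that answers directly. The whole-study tables leave out the switched children. The extension tables show them by sequence. The three-tier tables do not count their fesoterodine-period events as fesoterodine events.

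The objective says up to 24 weeks, so it does not require 24 weeks of exposure in every child. Switched children have a planned 12 weeks on fesoterodine. They can include children who left oxybutynin because they could not tolerate it and moved directly to fesoterodine (Protocol 5.2), a group of obvious safety interest.

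What is at stake is precision for uncommon harms, and a single clear denominator. The both-phases condition in SAP 5.3 adds a second gap: fesoterodine-randomised children who stop before the extension are outside the overall set as well. If some stop because of AEs, the rates in that set would tend to be low.

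**Working it through.** **Inputs from the documents.** SAP 4.1 plans for "approximately 99 subjects (33 evaluable subjects per arm) are evaluable at Week 12". Protocol 3 states: "Subjects will be randomized to each arm in a 1:1:1 ratio". That gives 66 children on fesoterodine and 33 on oxybutynin. The extension lasts 12 weeks. Protocol 5.1 says "it is expected that all subjects will also complete the extension phase" unless the investigator judges otherwise, but gives no rate.

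**Assumptions.** Continuation of oxybutynin children is taken as 50% to 100%. Early stopping among fesoterodine children is taken as 0% to 20%. Planned evaluable counts stand in for treated counts.

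**The plan's own figure.** The documents state no safety precision figure. The count of 33 per arm comes from the efficacy calculation: a 70 mL change, SD 120 mL, two-sided 5%. The noncentrality is 70/(120/√33) = 3.35. The one-sample t-test then has 90.1% power, and 33 is the smallest n that reaches 90%. The stated figure reproduces.

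**Share of exposed children who are switchers**, S/(66 + S), where S is the number switched:
- all continue: 33/99 = 33.3%
- 80% continue: 26.4/92.4 = 28.6%
- 50% continue: 16.5/82.5 = 20.0%

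**Share of fesoterodine person-weeks.** With full follow-up, 66 × 24 = 1584 and 33 × 12 = 396. The share is 396/1980 = 20%. With half continuing it is 198/1782 = 11%.

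**Zero-event one-sided 95% upper bound**, 1 − 0.05^(1/n), and **chance of at least one case of a 2% event**, 1 − 0.98^n:

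| Children | n | Upper bound | Chance, 2% event |
|---|---|---|---|
| Randomised to fesoterodine, doses pooled | 66 | 4.4% | 74% |
| Any fesoterodine, all switch, doses pooled | 99 | 3.0% | 87% |
| One dose, randomised | 33 | 8.7% | 49% |
| One dose, even split of switchers assumed | 50 | 5.8% | 64% |

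If only half continue, the pooled bound is 3.6% (n = 82.5) instead of 3.0%. The two-sided exact 95% limits for zero events are 5.4% (n = 66) and 3.7% (n = 99).

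**Person-time bound**, −ln(0.05)/T:
- 1584 weeks = 30.4 person-years, so 2.996/30.4 = 9.9 per 100 person-years
- 1980 weeks = 37.9 person-years, so 2.996/37.9 = 7.9 per 100 person-years

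**Effect of the both-phases condition.** If 10% of fesoterodine children stop before the extension, the overall set holds 66 × 0.9 = 59.4 and its bound is 4.9%. With all oxybutynin children switching, (99 − 59.4)/99 = 40% of exposed children are outside it. At 20% stopping the figures are 52.8, 5.5% and 46.7%.

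**The case against.** The strongest reply is that the overall set does what its label says. Its columns are 24-week columns serving a 24-week objective. Switched children have at most about 12 weeks on fesoterodine, follow another antimuscarinic, and have a dose chosen by the investigator. Putting them in those columns would mix unlike exposures. The 12-week primary objective is served by the active comparator phase set, which holds every treated fesoterodine-randomised child. All of this stands, and it is why the existing set should not be redefined.

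A reader might infer that up to a third of exposed children drop out of the safety analysis. The documents do not support that. Their AEs are tabulated in the extension columns, events of particular interest are plotted for that phase, and the other safety tables include these children. The 74% to 87% comparison therefore describes one table, not the chance that the report shows an event at all.

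It can also be said that the reader may simply add columns, since switched and fesoterodine-randomised children are different people. That works if the whole-study tables hold all fesoterodine-randomised children, as SAP 8.2.5 reads. Under SAP 5.3 the sum omits those who stopped early. Adding active comparator and extension columns instead can count a child twice.

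Finally, the SAP calls its safety analysis exploratory and sets no precision target, so no stated target is missed. That also stands, and it limits the weight of the point.

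**Conclusion.** The point holds as a gap in presentation. No planned analysis is invalid because switched children are shown separately, and keeping the 24-week group clean has real value. What is missing is one AE summary over all Cohort 1 children exposed to fesoterodine.

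The gain is moderate. The fall from 4.4% to 3.0% is a best case that needs every oxybutynin child to continue and both doses to be pooled, which the SAP does not plan for AEs. In person-time the switched children add a fifth of the total, not a third. For events arising after 12 weeks of fesoterodine they add essentially nothing. Actual continuation and early-stopping rates are not in the documents.

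An any-dose set would also bring in fesoterodine children who stop before the extension. That matters for bias as well as precision if SAP 5.3 is applied as written.

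**What to change.** - Keep the 24-week, randomised and by-sequence tables and plots unchanged.
- Add to SAP 5.3 and 8.2.5 a supplementary Cohort 1 'All fesoterodine exposure' AE summary. Include every subject with at least one fesoterodine dose in either phase. Count AEs from the first to the last fesoterodine dose plus the SAP's 7-day fesoterodine lag. Report by fesoterodine dose and in total: n, %, exact 95% CI and events per patient-week.
- State that the summary serves incidence and upper bounds, not dose comparison, because switched children have prior oxybutynin, at most about 12 weeks on fesoterodine and an investigator-chosen dose.
- Reconcile the both-phases condition in SAP 5.3 with SAP 8.2.5, so that it is clear whether fesoterodine children who stop early are in the whole-study tables.

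The cost is a short SAP revision and one extra set of AE tables from data already collected. The downside is mixed exposure length and history in the pooled columns. Patient-week rates address the length, and the stated limit on use addresses the rest.

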## **5. STUDY TREATMENTS**

### **5.1. Fesoterodine**

#### *Cohort 1 (Subjects >25 kg)*

Subjects randomized to fesoterodine will receive either 4 mg or 8 mg fesoterodine PR tablets once daily throughout the initial 12 weeks of the active comparator phase and will continue at the same dose during the 12 week safety extension phase. All those assigned to the fesoterodine 8 mg arm will start at 4 mg daily for one week, and will then escalate to 8 mg daily. If subjects cannot tolerate the dose they are randomized to they should be withdrawn from the trial as a dose reduction is not permitted in this trial.

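### The Cohort 1 whole-study safety set keeps only fesoterodine subjects who entered the extension, SAP 8.2.5 does not state that limit, and Cohort 2 has no whole-study set

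*SAP*

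**What the plan says.** SAP 5.3 gives Cohort 1 three sets for AE and duration-of-treatment summaries. Two are phase-specific and need one dose in that phase. The third, the overall study set, takes subjects randomised to fesoterodine who "received at least one dose of study medication during both phases of the study", and its two columns carry a 24-week label.

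A wider set, defined by a dose "at any time during the study (ie, in either phase", also exists. SAP 5.3 assigns it to all other safety tables, so not to AEs or duration.

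SAP 8.2.5 (Other Adverse Event Reporting) describes the whole-study AE displays differently: "These presentations will only include subjects who were randomised to fesoterodine". It mentions no extension dose and does not refer back to 5.3. It adds that plots of "adverse events of particular interest will be presented for the Safety Extension phase and for the study as a whole".

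For Cohort 2, SAP 5.3 opens with "There will be three safety analysis sets for Cohort 2", again for AEs and duration. It then lists an efficacy-phase set, an extension-phase set and the set for all other safety tables. SAP 8.2.5 nevertheless plans whole-study columns such as "Fesoterodine 2mg BIC (24 weeks", with a matching 4 mg column.

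Protocol 2.1.2 makes safety over a period of up to 24 weeks a secondary objective in each cohort. Protocol 9.3 defines the safety set by a dose in the relevant phase and has no both-phases set.

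**The concern.** Entry to the extension depends on how the first 12 weeks went. Protocol 5.1 says of fesoterodine subjects: "If subjects cannot tolerate the dose they are randomized to they should be withdrawn from the trial". Protocol 4.3 keeps out subjects whose urodynamics have worsened. Others leave for unrelated reasons. A set that requires an extension dose is therefore selected on a post-randomisation outcome that is partly a safety outcome.

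Three things are at stake:

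- The Cohort 1 whole-study AE tables and plots can understate cumulative incidence, and the whole-study duration summary overstates exposure if it is read as describing everyone treated.
- The 24-week label does not tell the reader that the columns hold only subjects who entered the extension.
- Because 5.3 and 8.2.5 describe the population differently, and Cohort 2 has none defined, two programmers could produce different 24-week tables from the same data.

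**Working it through.** **Which set serves which display**

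| Display | Population in SAP 5.3 | Population in SAP 8.2.5 |
|---|---|---|
| First-phase AEs and duration | any dose in that phase | consistent for AEs |
| Extension AEs and duration | any extension dose | consistent for AEs |
| Whole-study AEs, Cohort 1 | randomised to fesoterodine and dosed in both phases | randomised to fesoterodine |
| Whole-study duration, Cohort 1 | same both-phases set | not addressed |
| Whole-study AEs, Cohort 2 | none named | randomised to fesoterodine |
| All other safety tables | any dose in either phase | treatment groups only |

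Two points follow.

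1. In Cohort 1, subjects in the overall set are those in the two fesoterodine-to-fesoterodine columns of the extension set. The overall set adds these continuers' first-phase events but no further subjects.
2. In Cohort 2, three sets are announced for AEs and duration and two are named. Counting the set for all other safety tables would give three, but by the same count Cohort 1 would have four, and that set is not for AEs or duration.

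**Size of the effect (illustration only)**

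The documents give no early-stopping or AE rates. The only figure taken from them is 33 evaluable subjects per arm (Protocol 9.1), used here as the number dosed. Assumptions: d early stoppers per arm, from 3 to 7; AE rate pe in stoppers; AE rate pc in continuers, from 10% to 30%.

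All-dosed incidence is [(33 − d) × pc + d × pe] / 33, and the both-phases set shows pc. The gap is therefore (d/33) × (pe − pc).

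| Stoppers' AE rate | Smallest gap | Largest gap |
|---|---|---|
| same as continuers | 0 | 0 |
| 60% | (3/33) × (0.6 − 0.3) = 2.7 points | (7/33) × (0.6 − 0.1) = 10.6 points |
| 100% | (3/33) × (1.0 − 0.3) = 6.4 points | (7/33) × (1.0 − 0.1) = 19.1 points |
| 0% | (3/33) × (0 − 0.1) = −0.9 points | (7/33) × (0 − 0.3) = −6.4 points |

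A positive gap means the both-phases set understates incidence; a negative gap means it overstates it.

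For first-phase AEs that lead to withdrawal, the both-phases set shows zero by construction. If all d stoppers left for that reason, the all-dosed figure would be 3/33 = 9.1% to 7/33 = 21.2%.

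For mean exposure, assume stoppers leave at Week 4 and the rest reach Week 24. The all-dosed mean is [24 × (33 − d) + 4d] / 33:

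- d = 3: 22.2 weeks, 1.8 below the 24 shown by the both-phases set
- d = 5: 21.0 weeks, 3.0 below
- d = 7: 19.8 weeks, 4.2 below

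**The case against.** **The two sections can be read together.** SAP 8.2.5 states a necessary condition that removes oxybutynin starters, while 5.3 defines the sets and uses the same Cohort 1 labels, so 5.3 could be taken to govern. That is a fair reading, but 8.2.5 does not cite 5.3. If 5.3 does govern, the selected population is what gets reported.

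**Nothing is lost from the report.** This is correct. Early stoppers' AEs and first-phase duration are in the active comparator phase summaries, and the three-tier AE tables cover that phase. On withdrawals, 5.3 says: "All randomized subjects will be used for summarizing discontinuations in the Active Comparator Phase and overall". The whole-study display is an SAP addition, since Protocol 9.3 asks for presentations by phase. These points limit the finding to the whole-study AE and duration displays. They do not repair those displays: a subject with an event in both phases counts in both phase tables, so adding the tables does not give cumulative incidence.

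**The denominator of 33 is doubtful.** Protocol 9.1 means 33 evaluable at Week 12, so the number dosed may be nearer 33 + d. Using 36 to 40 dosed, the 60% case gives (3/36) × 0.3 = 2.5 to (7/40) × 0.5 = 8.8 points. The exposure gap, 20d/(33 + d), becomes 1.7, 2.6 and 3.5 weeks for d = 3, 5 and 7. The effect is somewhat smaller and the direction is the same.

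**Cohort 2 is a drafting gap.** This also stands. No both-phases rule is stated there, so no bias is shown; the population is simply unassigned.

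**The whole-study counting window may follow from the phase windows and sponsor standards.** It may. On its own this would be a request for detail, not an error.

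**Conclusion.** The concern holds and should be fixed. As written, SAP 5.3 removes from the Cohort 1 whole-study AE and duration summaries every fesoterodine subject who did not start the extension. These are the displays closest to the up-to-24-weeks objective. SAP 8.2.5 does not state that restriction, and the Cohort 2 whole-study columns have no defined AE or duration set.

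The existence of the defect rests on the text alone. Its size cannot be known from the documents: the incidence gap depends wholly on assumed stopping and event rates and can be zero or reversed. For exposure the direction is firmer, because subjects who never start the extension will in general have shorter treatment than those who do. No efficacy result is affected, and fesoterodine subjects who stop during the extension remain in the set.

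**What to change.** - In SAP 5.3, define the overall set for each cohort as all subjects randomised to fesoterodine who took at least one dose of fesoterodine in either phase. This matches the any-dose rule the SAP already uses for its other safety tables.
- Label the columns as up to 24 weeks.
- In SAP 8.2.5, name that set as the population for the whole-study tables and plots in both cohorts. State the AE counting window in line with the existing phase and lag rules, without a new cut-off.
- If a both-phases summary is still wanted, keep it as an extra display labelled as subjects who entered the extension.

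The cost is a few lines of SAP text, one population flag per cohort and relabelled columns. No new data are needed.
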